### **9.4.2 Statistical model, hypothesis, and method of analysis**

The statistical hypotheses for PASI 75 response at Week 12 and IGA 0 or 1 response at Week 12 being tested is that secukinumab (low or high dose) is not superior to placebo in the proportion of subjects with PASI 75 and IGA 0 or 1 response at Week 12.

Let  $p_j$  denote the proportion of PASI 75 responders at Week 12 for treatment group  $j$  and  $r_j$  denote the proportion of IGA 0 or 1 responders at Week 12 for treatment group  $j$ ,  $j=0, 1, 2$ , where

- 0 corresponds to placebo,
- 1 corresponds to secukinumab low dose,
- 2 corresponds to secukinumab high dose.

The following hypotheses will be tested

$$H_1: p_1 - p_0 \leq 0 \text{ versus } H_{A1}: p_1 - p_0 > 0,$$

$$H_2: p_2 - p_0 \leq 0 \text{ versus } H_{A2}: p_2 - p_0 > 0,$$

$$H_3: r_1 - r_0 \leq 0 \text{ versus } H_{A3}: r_1 - r_0 > 0,$$

$$H_4: r_2 - r_0 \leq 0 \text{ versus } H_{A4}: r_2 - r_0 > 0.$$

In other words:

$H_1$ : Secukinumab low dose is not superior to placebo with respect to PASI 75 response at Week 12

$H_2$ : secukinumab high dose is not superior to placebo with respect to PASI 75 response at Week 12

$H_3$ : secukinumab low dose is not superior to placebo with respect to IGA 0 or 1 response at Week 12

$H_4$ : secukinumab high dose is not superior to placebo with respect to IGA 0 or 1 response at Week 12

The primary analysis method will be the exact logistic regression with all 4 treatment groups (including etanercept); baseline bodyweight, age stratum and baseline PASI score as explanatory variables. Odds ratios will be computed for comparisons of secukinumab dose regimens versus placebo utilizing the logistic regression model fitted. Confidence intervals for risk difference will be derived based on the exact method.

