### 2.6.3 Statistical hypothesis, model, and method of analysis

The statistical hypotheses for PASI 75 response at Week 12 and IGA mod 2011 0 or 1 response at Week 12 being tested is that secukinumab (low or high dose) is not superior to placebo in the proportion of subjects with PASI 75 and IGA mod 2011 0 or 1 response at Week 12.

Let  $p_j$  denote the proportion of PASI 75 responders at Week 12 for treatment group  $j$  and  $r_j$  denote the proportion of IGA 0 or 1 responders at Week 12 for treatment group  $j$ ,  $j=0, 1, 2$ ,

where

- 0 corresponds to placebo,
- 1 corresponds to secukinumab low dose,
- 2 corresponds to secukinumab high dose.

The following hypotheses will be tested

$H_1: p_1 - p_0 \leq 0$  versus  $H_{A1}: p_1 - p_0 > 0$ ,

$H_2: p_2 - p_0 \leq 0$  versus  $H_{A2}: p_2 - p_0 > 0$ ,

$H_3: r_1 - r_0 \leq 0$  versus  $H_{A3}: r_1 - r_0 > 0$ ,

$H_4: r_2 - r_0 \leq 0$  versus  $H_{A4}: r_2 - r_0 > 0$ .

In other words:

$H_1$ : secukinumab low dose is not superior to placebo with respect to PASI 75 response at Week 12

$H_2$ : secukinumab high dose is not superior to placebo with respect to PASI 75 response at Week 12

$H_3$ : secukinumab low dose is not superior to placebo with respect to IGA mod 2011 0 or 1 response at Week 12

$H_4$ : secukinumab high dose is not superior to placebo with respect to IGA mod 2011 0 or 1 response at Week 12

The primary endpoint (PASI 75 and IGA mod 2011 0 or 1 response at Week 12) will be evaluated using an exact logistic regression model with treatment group, baseline body weight stratum, age stratum and baseline PASI score as explanatory variables (refer to the appendix “5.1.2.2 Exact Logistic regression” for more details).

If exact logistic regression model does not converge, then the following steps will be performed:

- If convergence not reached, remove the covariates from the model one by one until convergence is reached; start with removing continuous covariates (i.e., baseline PASI), followed by removing categorical covariates (i.e., age, bodyweight strata);
- If convergence not reached at all, then perform Fisher’s exact test.

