### 3 Sample size calculation

Approximately 160 pediatric subjects from 6 to less than 18 years of age, with 2 subgroups: 6 to less than 12 years of age, and 12 to less than 18 years of age. Stratification is planned for age (<12 years,  $\geq$ 12 years) and weight (<25kg, 25-<50kg and  $\geq$ 50kg). It will be targeted to have at least 30 subjects in the <12 years subgroup at a minimum. Enrollment of children aged 6 to less than 12 years will proceed after efficacy and safety data for approximately 80 (approximately 40 treated with AIN) enrolled adolescents (aged 12 to less than 18 years) treated for 28 weeks have been reviewed and deemed satisfactory by a Data Monitoring Committee.

Since two secukinumab dose regimens will be tested versus placebo with respect to the coprimary endpoints (PASI 75 response and IGA 0 or 1 response at Week 12), the type-I-error will be split to 1.25% one-sided for each comparison. With 40 subjects per group and assuming a response rate of 10% for PASI 75 response and IGA 0 or 1 response in the placebo group, the power to show a response rate of 65% for PASI 75 response and 45% for IGA 0 response in the secukinumab groups based on Fisher's exact test (nQuery Advisor 7.0, two group Fisher's-exact test of equal proportions) is approximately 99% for PASI 75 response and approximately 88% for IGA mod 2011 0 or 1 response. For the secondary endpoint of PASI 90 response at week 12, assuming a response rate of 8% in the placebo group, the power to show a significant difference between a secukinumab dose and placebo, assuming a response rate of 39% in the secukinumab groups based on Fisher's exact test (nQuery Advisor 7.0, two group Fisher's-exact test of equal proportions) is approximately 82% for PASI 90 response. The assumed response rates for secukinumab are based on the confirmatory efficacy in severe patients in the adult phase III program. At Week 12, PASI 75 response rates of 11% and PASI 90 response rates of 7% have been reported in the placebo group in [Paller et al \(2008\)](#) for children and adolescents aged 4-17 years.

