### 5.1.2.2 Exact Logistic regression

Selected binary outcome variables including PASI 50 / 75 / 90 / 100 response and IGA mod 2011 0 or 1 response, will be evaluated using an exact logistic regression model with treatment regimen, age category, baseline body weight category and baseline score for the response variable. Remove “baseline score for the response variable” from the exact logistic regression model, if model doesn’t converge or have insufficient SAS memory issue while executing the model. Odds ratios will be computed for comparisons of secukinumab dose regimens versus control(s) utilizing the exact logistic regression model fitted.

Additional exact logistic analysis will be performed for IRT dosing error subjects, using both multiple imputation and pure non-responder imputed records.

If response rates are 0% or 100% in one of the treatment groups then odds ratio estimates and p-values will not be displayed in outputs, but “-” will be shown.

The odds ratio will be calculated such that an odds ratio  $> 1$  is favorable for secukinumab. Using PROC GENMOD with EXACT statement to calculate the confidence interval for the odds ratios conditional on all other parameters specified in MODEL statement. The 95% confidence interval for the regression parameter of the active treatment effect relative to control(s) will be calculated using an exponential transformation to create the confidence interval for the odds ratio.

All p-values reported on linear hypotheses about regression coefficients will be based on the exact tests in the SAS procedure PROC GENMOD with EXACT statement.

For superiority hypotheses, one sided p-value will be calculated by dividing the two-sided p-value by half (i.e., “p/2”) if treatment effect is in favor of secukinumab dose regimens and calculated by “1-p/2” if treatment effect is in favor of Control.

Exact logistic regression will be applied to response variables at each visit.

If exact logistic regression model does not converge, then the following steps will be performed:

- If convergence not reached, remove the covariates from the model one by one until convergence is reached; start with continuous covariates (i.e., baseline PASI), followed by removing categorical covariates (i.e., age, bodyweight strata);
- If convergence not reached at all, then perform Fisher’s exact test.

It should be noted that this model might not converge if response rates are too low.

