  ELSE IF <baseline IGA>=2 THEN DO;
    IF <IGA per week primary endpoint> < 0.5 THEN <IGA 0/1 response> =1;
    ELSE IF <IGA per week primary endpoint> >=0.5 THEN <IGA 0/1 response> =0;
    ELSE PUT "E" "RROR:" stysid1a=;
  END;
  ELSE <IGA 0/1 response> =0;
RUN;
```

The treatment differences for each imputed data set will then be evaluated by exact logistic regression and ODDS ratio as described in [Section 5.1.2.2](#). This analysis will be done by `_IMPUTATION_` for the comparison to the placebo treatment group. The model should be estimating response probability = 1 by using DESECENDING option. Using the EXACT statement in the GENMOD procedure and the ODS OUTPUT data set “ExactOddsRatio” provides the exact estimate for the odds ratio and confidence intervals.

```
PROC GENMOD <option>;
  CLASS <stratum> <treatment>(ref="")/ param=ref;
  MODEL <response> = <explanatory variables> / link=logit dist=bin type3;
  BY <by-variables>;
  EXACT <treatment>/ ESTIMATE=both ;
  ODS OUTPUT ExactOddsRatio =Estimates;
RUN;
```

The MIANALYZE procedure expects the parameter estimate in the variables ESTIMATE. No standard error estimate for odds ratio will be provided in “Estimates” dataset.

```
Data <modified dataset>;
```

```
set Estimates;
ESTIMATE=Estimate;

if missing(ESTIMATE) then delete;
RUN;
```

The estimates and standard errors of the log (odds ratio) based on the 100 imputed data are then combined by applying Rubin's rules for multiple imputed data sets, see [Little and Rubin \(2002\)](#).

Programming notes:

- The variables ESTIMATE in the input data set for the MIANALYZE procedure may not be missing. Records with missing values need to be deleted and the variable \_IMPUTATION\_ needs to be renumbered and regenerated since for each by group the procedure expects consecutive numbers starting at 1.
- The ESTIMATE and STDERR in terms of odds ratios from logistic regressions will be transformed to follow a normal distribution before MIANALYZE procedure. They will be transformed back to Odds Ratio to get the corrected ESTIMATE and corresponding CIs.

The SAS procedure MIANALYZE will be applied as follows:

Step 1:

```
DATA <modified dataset_t>;
SET <modified dataset>;
stderr= stderr;
VARIABLE="estimate";
RUN ;

ODS LISTING CLOSE;
ODS OUTPUT ParameterEstimates=<results> VarianceInfo=<varinfo> ModelInfo=<modelinfo>;
PROC MIANALYZE PARMS=<modified dataset>;
BY <by-variables>;
MODELEFFECTS ESTIMATE;
RUN;

ODS LISTING;
data <results_back>;
set <results>;

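### SAP 5.1.2.2 contradicts 2.6.3 on the baseline covariate for co-primary IGA 0/1, the fallback rules conflict, and nothing requires one model across the 100 imputations

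*SAP*

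**What the plan says.** **Covariates.** Protocol 9.4.2 specifies exact logistic regression with "baseline bodyweight, age stratum and baseline PASI score as explanatory variables". SAP 2.6.3 uses weight stratum, age stratum and baseline PASI for both co-primaries and refers to 5.1.2.2 for details. SAP 5.1.2.3, which governs the multiple-imputation analysis, also names baseline PASI for PASI 75 and IGA 0/1 together. SAP 5.1.2.2 instead lists treatment, age category, "baseline body weight category and baseline score for the response variable".

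**Fallback.** On non-convergence, SAP 2.6.3 says to "remove the covariates from the model one by one until convergence is reached": baseline PASI first, then the age and weight strata, then Fisher's exact test. SAP 5.1.2.2 repeats that list, but also has a separate rule that removes the baseline score if the model fails to converge or should "have insufficient SAS memory issue while executing the model". SAP 5.1.2.3 answers non-convergence with a pooled risk difference.

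**Imputation.** SAP 5.1.2.3 fits the model in each of 100 imputed data sets and pools the log odds ratios by Rubin's rules. A programming note there says "Records with missing values need to be deleted and the variable" that numbers the imputations is then regenerated.

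**The concern.** IGA 0/1 is one of two endpoints that must both succeed for a dose. A programmer working from 2.6.3 and one working from 5.1.2.2 would fit different models to it. Under 5.1.2.2 the baseline adjustment does almost nothing: entry requires an IGA of 4, and 5.1.2.3 leaves baseline IGA out of the imputation model for that reason.

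The fallback is foreseeable. SAP 5.1.2.2 warns that the model may not converge at low response rates, and the planned placebo rate of 10% means about 4 responders among 40. The same failure then has several prescribed responses: drop one covariate, step down to Fisher's test, report a risk difference, or delete the imputation.

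Odds ratios are non-collapsible: with and without a prognostic covariate they measure different quantities, even in a randomised comparison. If some imputations used the full model and others a reduced one, Rubin's rules would average two quantities and count the gap between them as missing-data uncertainty. If failed imputations are simply deleted, the result rests on those data sets that happened to fit.

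**Working it through.** **1. The plan's own figures.** SAP section 3 states that "the type-I-error will be split to 1.25% one-sided for each comparison". Its other inputs are "With 40 subjects per group and assuming a response rate of 10% for PASI 75 response" (10% also for placebo IGA 0/1) and a "response rate of 65% for PASI 75 response and 45% for IGA 0 response in the secukinumab groups"; for PASI 90 it assumes 8% against 39%. Power of Fisher's exact test by full enumeration is the sum over (x1, x0) of Bin(x1; 40, p1) × Bin(x0; 40, p0), restricted to tables with one-sided p ≤ 0.0125.

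| Endpoint | Stated | Recomputed |
|---|---|---|
| PASI 75 | about 99% | 99.9% |
| IGA 0/1 | about 88% | 88.4% |
| PASI 90 | about 82% | 82.1% |

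These reproduce. They belong to an unadjusted test, so the covariate question does not touch the sample size.

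**2. The sections side by side.**

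| Section | Baseline covariate for IGA 0/1 | Trigger | Response |
|---|---|---|---|
| Protocol 9.4.2 | PASI | none stated | none stated |
| SAP 2.6.3 | PASI | non-convergence | PASI out, then strata, then Fisher |
| SAP 5.1.2.2, opening rule | baseline of the response variable, i.e. IGA | non-convergence or memory | baseline score out |
| SAP 5.1.2.2, later list | PASI | non-convergence | as 2.6.3 |
| SAP 5.1.2.3 | PASI | non-convergence | risk difference |
| SAP 5.1.2.3, programming note | – | missing estimate | delete the imputation |

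For PASI endpoints the two covariate descriptions coincide. The contradiction is confined to IGA 0/1.

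**3. What dropping baseline PASI does to the odds ratio.** Model: logit P(response) = a(arm) + βz, with z standard normal. For each arm, solve for the intercept a that makes the average of expit(a + βz) over z equal the planned rate. The adjusted odds ratio is exp(a1 − a0). The unadjusted one is (0.45/0.55)/(0.10/0.90) = 7.36 whatever β is. The documents give no β, so it is assumed.

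| β per SD | a0 | a1 | Adjusted | Unadjusted |
|---|---|---|---|---|
| 0 | −2.197 | −0.201 | 7.36 | 7.36 |
| 0.3 | −2.233 | −0.205 | 7.6 | 7.36 |
| 0.5 | −2.295 | −0.213 | 8.0 | 7.36 |
| 0.8 | −2.439 | −0.229 | 9.1 | 7.36 |

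At β = 0.5 the same calculation gives 19.1 against 16.71 for PASI 75, and 7.94 against 7.35 for PASI 90.

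**4. What a mixture would do.** Illustrative simulation: 40 per arm, IGA rates of 10% and 45% set at the covariate mean, an assumed 5% missing, 100 imputations, 40 replicates, and ordinary logistic fits in place of exact ones. B is the between-imputation variance and T the total variance.

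| β | Share reduced | Pooled log OR | OR | B | T | log OR/√T |
|---|---|---|---|---|---|---|
| 0.5 | none | 2.177 | 8.82 | 0.030 | 0.537 | 2.97 |
| 0.5 | half | 2.109 | 8.24 | 0.043 | 0.528 | 2.90 |
| 0.5 | all | 2.040 | 7.69 | 0.025 | 0.487 | 2.92 |
| 1.0 | none | 2.233 | 9.33 | 0.033 | 0.531 | 3.06 |
| 1.0 | half | 2.078 | 7.99 | 0.068 | 0.511 | 2.91 |
| 1.0 | all | 1.922 | 6.83 | 0.020 | 0.407 | 3.01 |

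The mixed estimate lies between the two models, and B exceeds that of either pure analysis. The last column uses averaged quantities and is only a guide. Every entry is well above 2.24, the normal critical value for 1.25% one-sided.

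**The case against.** The strongest reply is that this is one loose phrase. Baseline PASI is named in Protocol 9.4.2, 9.4.4 and 9.5.2 and in SAP 2.6.3, 2.7.3 and 5.1.2.3, and 5.1.2.2 itself later gives baseline PASI as the continuous covariate. That stands, and it rules out reading the primary model as open in general. It does not remove the contradiction for IGA 0/1, because 5.1.2.2 is where 2.6.3 sends the reader.

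A reader might also infer that different models were in fact pooled. The documents do not support that. The template in 5.1.2.3 is a single call with one model statement, run by imputation. It applies one covariate list throughout, and mixing would need code that the SAP does not contain. What the text does prescribe for a missing estimate is deletion, which conflicts with the stepwise fallback.

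A reader might further infer that the confirmatory conclusion depends on the computer or that false positives increase. Neither is shown. The triggers are computational and do not depend on the size of the treatment effect; the removal order is largely pre-specified; with no treatment effect both models target an odds ratio of 1; and the larger between-imputation variance points towards caution rather than false positives.

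Finally, simply deleting the memory clause would leave an exact model that cannot be executed with no rule at all. That objection is right, and the fix below keeps the clause within a common rule.

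**Conclusion.** The point holds as a contradiction within the documents on the model for one co-primary endpoint, together with conflicting fallback rules and no requirement for a common model across imputations. That pooling could mix models is a possibility the text leaves open, not something the documents show to have occurred.

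The size depends on how strongly baseline PASI predicts response, which the documents do not state. Under the assumed effects of 0.3 to 0.8 log-odds per SD, the IGA odds ratio differs by 0.2 to 1.8 (7.6 − 7.36 to 9.1 − 7.36, rounded) between the full model and one without baseline PASI. If the effect is weak, the difference is negligible. This bears on the estimate and its interpretation. No change in significance, planned power or sample size has been demonstrated.

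**What to change.** 1. In SAP 5.1.2.2, replace the last item of "baseline body weight category and baseline score for the response variable" with baseline PASI score, for all endpoints.
2. Define one failure condition covering non-convergence and inability to execute, including lack of memory, and use the single removal order already in 2.6.3.
3. If the model fails in any imputed data set, use the same reduced model in all 100 data sets, for both doses of that endpoint and in its non-responder analysis. Remove the instruction to delete failed imputations.
4. Report the number of failed fits and the model finally used, by endpoint.
5. State how the last step is combined across imputations. SAP 2.6.3 ends in Fisher's exact test but gives no way to pool its p-values; 5.1.2.3 pools only the risk difference.

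The cost is SAP wording and possibly a rerun. The statistical downside is a slight loss of precision if one failure removes baseline PASI everywhere. The Week 24 database is already locked (data cut-off 7 March 2019; SAP amendment 3.0 is dated 18 December 2020), so any rerun must be labelled post hoc. Disclosing the model used and the failed fits for the analysis already done requires no new analysis.

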## 2 Statistical methods

## 2.1 Data analysis general information

This document covers the statistical analysis plan for Week 24 PEA analysis, Week 52 analysis and final analysis.

█████ will perform the analyses at week 24 and week 52 and final analysis. Statistical software SAS version 9.4 or later will be used.

Summary statistics for continuous variables will be presented with n, mean, standard deviation, minimum, lower quartile (Q1), median, upper quartile (Q3) and maximum for observed values and change from baseline. Summary statistics for discrete variables will be presented in contingency tables and will include absolute and relative frequencies.

P-values will be presented as one-sided for hypothesis testing and as two-sided for other analysis. Two-sided 95% confidence intervals will be displayed. If not otherwise specified, hypothesis testing will be based on one-sided p-values that the treatment effect is in favor of secukinumab. The level of significance will be set to 2.5% (one-sided, family-wise type-I-error). The 95% confidence intervals will not be used for decision making; they will only be used for estimation and will therefore always be two-sided.

All listings will be presented by treatment sequence.

Footnotes will generally be provided for

- abbreviations used in the output; abbreviations used on several outputs, e.g. for listings can be presented on a separate page and do not have to be repeated as footnotes on each listing
- sort order of categories, e.g. for sorting within MedDRA (Medical Dictionary for Regulatory Activities) hierarchy levels
- MedDRA version used for reporting of MedDRA coded data

Footnotes will generally NOT be given for

- units displayed on the output
- interpretation of results (e.g. “odds ratio larger than 1 favors active treatment”)
- information that can be retrieved from the statistical section of the CSR unless it is not identifiable from the output, e.g. explanation of analysis model used unless results of more than one model are displayed on an output
- derivations of variables (e.g. body mass index (BMI) will not be explained in a footnote)
- information that will be provided in the clinical study protocol and/or methods section of the CSR (e.g. baseline definition if this is specified in the statistical section of the CSR)

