Odds ratios will be computed for comparisons of secukinumab dose regimens versus placebo utilizing the exact logistic regression model fitted. In case of response rates of 0% or 100% in one of the treatment groups, for analyses with multiple imputation, confidence intervals for risk difference and p-values from the t-test for the risk difference comparing to 0 will be provided; for analyses with pure non-responder imputation, Fisher’s exact test will be applied and confidence intervals for risk difference will be provided.

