#### **Secondary variable:**

H5: secukinumab low dose is not superior to placebo with respect to PASI 90 response at Week 12

H6: secukinumab high dose is not superior to placebo with respect to PASI 90 response at Week 12

The graphical approach of Bretz (Bretz et al 2009) for sequentially rejective testing procedures is used to illustrate the testing strategy in Figure 2-1.

**Figure 2-1** Testing strategy

One-sided p-values will be derived. The family-wise error will be set to  $\alpha=2.5\%$  (one-sided). The hypotheses are mapped into two sets (H1, H3 and H5) or (H2, H4 and H6) such that hypotheses within a set correspond to the same secukinumab (AIN457) dose regimen. In essence, the type-I-error probability will be equally split for both sets of hypotheses and within each set, the hypothesis will be tested sequentially as follows:

Within each pair, of hypotheses (H1 or H3) and (H2 or H4), each hypothesis is tested at  $\alpha/2$  (one-sided). Only if both hypotheses of a pair are rejected, then the testing sequence will continue.

In the next step of the sequence, the null hypotheses corresponding to the PASI 90 comparison of secukinumab (AIN457) versus placebo will be tested. H5 and H6 will be tested at  $\alpha/2$  (one-sided).

If all hypotheses within a set referring to a secukinumab dose regimen are being rejected, i.e., either (H1, H3 and H5) or (H2, H4 and H6), then the corresponding type I error probability can be passed on to the other set of hypotheses, and if needed, hypotheses can be retested at a higher significance level.

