estimate=exp(ESTIMATE);
LCLMEAN=estimate*exp(-1.96*stderr);
UCLMEAN=estimate*exp(+1.96*stderr);
RUN ;
```

In case if exact logistic regression does not converge and risk difference estimates will be provided. The SAS procedure PROC FREQ for risk difference estimates will be applied as follows:

```
ODS LISTING CLOSE;
PROC FREQ DATA=<Imputed dataset> ORDER=DATA;
  TABLES <treatment group>*<response variable>/riskdiff fisher alpha=0.05;
  BY <By-variables>;
  ODS OUTPUT RiskDiffCol1=RiskDiffCol1 FishersExact=fisherexact;
RUN;

ODS LISTING;
DATA DRISK; SET RiskDiffCol1;
  WHERE control="1";
  ESTIMATE=risk;
  STDERR=ase;
  effect="Riskdiff";
```

```
IF missing(ESTIMATE) OR missing(STDERR) THEN DELETE;  
RUN;  
  
PROC SORT DATA=DRISK; BY <By-variables>; RUN;  
ODS LISTING CLOSE;  
ODS OUTPUT ParameterEstimates=results VarianceInfo=varinfo ModelInfo=Modelinfo;  
PROC MIANALYZE PARAMS=drisk;  
  by <By-variables>;  
  modeleffects Riskdiff;  
  stderr ase;  
RUN;  
  
ODS LISTING;  
DATA results2;  
  set results;  
  or=estimate*100;  
  lowercl=(LCLmean)*100;  
  uppercl=(UCLmean)*100;  
  KEEP <response variable> <By-variables> or lowercl uppercl probt;  
RUN;
```

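### The SAP's rule of halving a two-sided p-value does not give the one-sided exact p for Fisher's test when arms are unequal, and the risk-difference code lacks the one-sided conversion

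*SAP*

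**What the plan says.** **Level and sidedness.** SAP 2.1 states that, unless specified otherwise, "hypothesis testing will be based on one-sided p-values that the treatment effect is in favor of secukinumab". The testing strategy in SAP 2.7.2 repeats this for H1 to H6: "One-sided p-values will be derived". SAP 3 adds that "the type-I-error will be split to 1.25% one-sided for each comparison". A level of 2.5% becomes available to one dose after all hypotheses for the other dose are rejected.

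**How the one-sided p is obtained.** The only conversion rule is in SAP 5.1.2.2: the "one sided p-value will be calculated by dividing the two-sided p-value by half" if the effect favours secukinumab, and one minus that half otherwise. The same section bases its p-values on the exact tests of the logistic procedure and names Fisher's exact test as the last fallback.

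**Where exact single-dataset tests are used.** SAP 2.6.5 applies the exact logistic model with non-responder imputation as the sensitivity analysis. SAP 2.6.3 replaces it with Fisher's test if an arm has 0% or 100% response.

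**Multiple imputation.** In SAP 5.1.2.3 the primary method combines log odds ratios from 100 imputed datasets by Rubin's rules. If an arm has 0% or 100% response, SAP 2.6.3 says that "confidence intervals for risk difference and p-values from the t-test for the risk difference comparing to 0 will be provided". The risk-difference code in 5.1.2.3 ends with "KEEP <response variable> <By-variables> or lowercl uppercl probt".

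**The concern.** An exact test is chosen for its guarantee: given the total number of responders, the chance of a false rejection does not exceed the nominal level. That guarantee belongs to the one-sided tail probability itself. Fisher's usual two-sided p is not twice that tail. It adds only those tables in the opposite tail that are no more likely than the observed one. If the arms differ in size the null distribution is skewed, the opposite tail can add little or nothing, and half of the sum falls below the true one-sided p. A result can then pass 1.25% when its exact one-sided p does not.

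The pooled risk difference has a different gap. The code outputs a two-sided p with no conversion and no check of direction, so someone who follows the template literally would carry the wrong quantity into the comparison with 1.25%.

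**Working it through.** **Inputs.** 40 per group; 65% against 10% (PASI 75), 45% against 10% (IGA 0/1), 39% against 8% (PASI 90); one-sided 1.25% (SAP 3). Allocation 1:1:1:1, about 160 subjects, stratified by age and weight (SAP 1.1). Unequal arms such as 40 and 41 are my assumption; the documents do not promise exactly equal arms.

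**1. The plan's own figure.** Power is the sum of binomial probabilities over all tables with one-sided hypergeometric p ≤ 0.0125, at 40 against 40. Result: 99.9%, 88.4% and 82.1%, against the stated 99%, 88% and 82%. At 0.625% it would be 99.8%, 81.7% and 74.1%. So the plan's level is one-sided 1.25%.

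**2. Halving at 11/40 (secukinumab) against 3/41 (placebo).** With 14 responders among 81 subjects, X, the number on secukinumab, is hypergeometric.
- One-sided p = P(11) + P(12) + P(13) + P(14) = 0.013516 + 0.002513 + 0.000271 + 0.000013 = 0.0163.
- Opposite-tail tables no more likely than 0.013516 are X = 0, 1, 2: 0.000019 + 0.000387 + 0.003379 = 0.0038. X = 3 has probability 0.0171 and is left out.
- Two-sided p = 0.0163 + 0.0038 = 0.0201; halved, 0.0100.

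The true one-sided p does not reach 1.25%; the halved p does.

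**3. Further tables.**

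| Table | One-sided p | Two-sided p | Halved |
|---|---|---|---|
| 8/40 vs 1/41 | 0.0131 | 0.0145 | 0.0072 |
| 5/39 vs 0/41 | 0.0239 | 0.0239 | 0.0120 |
| 11/40 vs 3/40 | 0.0184 | 0.0367 | 0.0184 |

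In the second row the opposite extreme (0/39 vs 5/41, probability 0.0312) is more likely than the observed table, so the opposite tail adds nothing. This table has a 0% arm, the case in which SAP 2.6.3 sends the non-responder analysis to Fisher's test. Given five responders, the halved rule rejects under the null with probability 0.0239 instead of at most 0.0125. In the third row the arms are equal, the distribution is symmetric, and halving is exact.

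**4. How many tables change decision at 1.25%.** Full enumeration (secukinumab arm first): none at 40 vs 40, 13 at 40 vs 41, 14 at 39 vs 41, 15 at 42 vs 40. The largest unconditional size of the halved rule over all common response rates is about 1.1%. At the planning rates and 40 vs 41, the tables that change have total probability 0.04% (PASI 75), 2.7% (IGA 0/1) and 3.4% (PASI 90). These figures apply only if Fisher's test is the route taken.

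**5. Pooled risk difference.** I use the complete-data Wald z as a stand-in for the pooled t, assuming little missing data. A p left unhalved would change the decision only for z between 2.241 and 2.498. With placebo at 0/40 and secukinumab at 5/40: difference 0.125, standard error √(0.125 × 0.875 / 40) = 0.0523, z = 2.39, two-sided p 0.0168, one-sided 0.0084. At 4/40 neither version rejects (0.0350, 0.0175); at 6/40 both do (0.0079, 0.0039). The chance of placebo 0/40 is 0.90^40 = 1.5% or 0.92^40 = 3.6%.

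**The case against.** **The SAP already fixes sidedness.** Sections 2.1 and 2.7.2 require one-sided p-values, and nothing says that Fisher's two-sided p must be halved rather than its one-sided p read off. This has weight. But 5.1.2.2 is the only place that says how a one-sided p is formed, it is worded for superiority hypotheses generally, and Fisher's test is named in the same section without a rule of its own. Halving is the natural reading.

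**The primary analysis is not touched.** This stands. The pooled log odds ratio is referred to a symmetric t or normal distribution, so halving is correct there. A one-sided exact tail could not replace it, since the SAP gives no rule for combining 100 tail probabilities.

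**Software behaviour is not shown.** This also stands in part. If the exact logistic output doubles a tail, halving recovers the one-sided p. The documents do not settle this, and the enumeration covers unstratified Fisher tables only, not the covariate-adjusted model.

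**A stronger reading.** A reader might infer that the plan compares an unhalved t-test p with 1.25%, so that it tests at one-sided 0.625% and loses power: 93.5% to 89.9% for IGA 0/1 and 89.8% to 84.7% for PASI 90 on a Wald test. The documents do not support this. No section compares a two-sided p with 1.25%. The exact logistic template has no halving line either, so its absence from the risk-difference template does not set the routes apart. Those losses also assume that every trial takes the risk-difference route, and an unhalved p would be conservative.

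**Conclusion.** The halving rule is wrong as a general rule for exact tests and should be changed. It affects the Fisher fallback and, unless the software's two-sided p is a doubled tail, the exact tests in the non-responder sensitivity analysis. It does not affect the Rubin-pooled primary p.

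The size is modest. Individual borderline tables are misjudged (0.0163 reported as 0.0100), and the conditional error given the number of responders can reach nearly twice nominal (0.0239 at 39 vs 41 with five responders). Yet unconditional size stays below 1.25%, and at exactly 40 vs 40 nothing changes. So this is a loss of the conditional guarantee and not an inflation of the trial's overall type I error. It rests on slightly unequal arms and on Fisher's two-sided p in its usual form.

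The bare `probt` is a code line to bring under the SAP's own one-sided rule, not a second alpha level.

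**What to change.** In SAP 5.1.2.2 and 2.6.3, state that for Fisher's test and for exact logistic p-values from a single dataset the one-sided exact tail in favour of secukinumab is taken directly. Limit the halving rule to Rubin-pooled t or normal p-values: p/2 if the estimate favours secukinumab, 1 − p/2 otherwise. In the risk-difference code of 5.1.2.3, add before the KEEP statement a line that sets the reported p to `probt`/2 if the pooled difference is above 0 and to 1 − `probt`/2 otherwise.

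The same edit should settle the fallback route. For non-convergence, 2.6.3 and 5.1.2.2 name Fisher's test while 5.1.2.3 gives pooled risk differences. For 0% or 100% response under multiple imputation, 2.6.3 gives a t-test p while 5.1.2.2 shows a dash for the odds ratio and p-value.

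The cost is a few sentences and one line of code, with no change to design or conduct. The downside is that some exact p-values become slightly less favourable to secukinumab.
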